# **Research Design & Methods**

Subjects who are candidates for lumbar spinal fusion with interbody support will be screened for inclusion in the study. All procedures are approved by the FDA (see appendix A for approved labeling) and are common practice at NYULMC. If the subject meets all of the eligibility criteria

PI: [name]

and agrees to participate in the study after informed consent, they will be enrolled into one of the three arms.

An enrollment ratio of BMAC + allograft to BMP to Autograft with bone marrow aspirate (control) (1:1:1) for a total of 60 subjects to be enrolled in the study. The study will determine and compare differences in fusion rate and health related quality of life parameters at 6 weeks, 3 months, 6 months, 1 year, and 2 years postoperatively.

### Intervention

Patients will receive a lumbar fusion with one of the three interbody support grafts listed below:

• INFUSE rhBMP-2 Bone Graft used according to its approved FDA labels, both the original approval performed from an anterior approach using titanium cages as well as the more recent approvals with the use of PEEK cages from a posterior interbody approach. BMP will be placed in a PEEK cage and to be inserted in a posterior or anterior approach;

or

• Allograft infused with adult stem cells from the bone marrow aspirate concentrate harvested from the iliac crest. Harvest® BMAC System delivers high stem cell concentration to the graft site and will be used according to its approved FDA label.

or

- Autograft with bone marrow aspirate (control)
- Enrollment will be 1:1:1
- The study will determine and compare differences in fusion rate and health related quality of life parameters at 6 weeks, 3 months, 6 months, 1 year, and 2 years postoperatively.
- Pre-operative standard care measures include narcotics usage and health-related quality of life measures: Oswestry Disability Index (ODI), Visual Analog Scale (VAS), Euro-Qol 5-dimension (EQ-5D), Health State Scale, PCS, PROMIS Surveys outlined below:
- PROMIS Bank V11 Pain Interference (Adaptive)
- PROMIS Scale v1.0 Pain Intensity 3a(Auto-scoring)
- PROMIS Bank v1.2 Physical Function(Adaptive)
- PROMIS Bank v2.0 Mobility(Adaptive)PROMIS Bank v2.0 Upper Extremity
  \* While PROMIS will be collected, it will be optional in this study due to limitation of getting patients to collect PROMIS at enrolling surgeon's site. Data will be collected from pre-operative standard-care measures for this study
- Intra-operative standard care measures include intra-operative and peri-operative blood loss, length of stay in hospital, bone marrow quality, and complications. Data will be collected from intra-operative and peri-operative standard care measures for this study.
- Post-operative standard care measures include fusion status at 1 year via CT scan, and health-related quality of life measures previously defined via RedCAP, radiological outcomes, and complications. Data will be collected from post-operative standard care measures for this study
- The radiologist will be blinded to the patient's treatment at the time of postoperative outcomes analysis. The patients will not be blinded to their assigned treatment arm.

PI: [name]

- Outcome measures will include:
  - 1. Pre-operative measures: narcotic usage, and health-related quality of life measures previously definedIntra-operative measures: intra-operative and perioperative blood loss, length of stay, complications
  - 2. Post-operative measures: fusion status at 1 year via CT scan, and health-related quality of life measures previously defined, length of stay, radiological outcomes, complications
- The patient and reviewer [of the clinical outcomes as well as the radiographic analysis postoperatively] will be blinded to the patient's treatment.

All materials procured from Harvest® BMAC System is FDA approved:

- Collection of Bone Marrow Aspirate Concentration (autologous adult stem cells) for Fusion
  - Bone Marrow Aspirate (BMA) will be aspirated from the anterior iliac crests using an 11 gauge 5 side-hole Jamshidi needle and a 60 mL syringe flushed with heparinized saline. Following a midline incision, the needle will be directed at about 30° to the vertical and parallel to the plane of the crest and inserted to a depth of approximately 5 to 8 cm (Figure 1). 1 mL will be sent for cellular analysis.

Figure 1

- Sixty mL of BMA will be aspirated while rotating and slowly withdrawing the needle toward the cortex. This step will be repeated on the contralateral ileum for a total of **60**, **120**, **or 180** mL of BMA. The BMA is then pooled into a blood bag containing Anticoagulant Citrate Dextrose Solution (ACD-A).
- The BMA will then be placed into the SmartPrep® Bone Marrow Concentrate (BMACTM, Harvest Technologies Corp., Plymouth, MA) system and concentrated in 15 minutes to a final volume of **10**, **20**, **or 30 mL**.
- The BMAC will then be combined with packed allograft cancellous bone chips using the Graft Delivery Pack (GDP, Harvest Technologies Corp.) yielding two or three 10 mL surgeon constructed bone logs (Figure 2). The allograft bone will be obtained routinely from the bone bank in the operating suite.

PI: [name]

Figure 2

• The allograft logs will be placed in the lateral gutter and interbody cages.

## **BMAC** dosing estimate for the lumbar spine

- If using Harvest Graft Delivery Kit:
  - o 1-level fusion: 10 cc of BMAC from 60 cc of BMA (roughly 10 cc of graft)
  - o 2-level fusion: 20 cc of BMAC from 120 cc of BMA
  - o 3-level fusion: 20 cc of BMAC from 120 cc of BMA
  - o 4-level fusion: 180 cc kit
  - o 5-level fusion: 240 cc kit
    - BMAC to graft ratio will be 1:1
- If not using Harvest Graft Delivery Kit:
  - Volume of BMAC will be slightly increased (some BMAC will not get directly into hydrating the graft as the BMAC would get lost in the hydration process and left in mixing bowls)

#### rhBMP-2 Fusion

- Two mL of BMA will be aspirated in identical procedure to the BMAC group for comparison of aspirate quality.
- For patients selected to receive BMP, 12 mL BMP will be applied at the surgical site of the interbody fusion using a collagen sponge following manufacturer's directions.
- BMP kit use per level:
  - o 1 Level Fusion: Extra small kit (1.4 cc)
  - o 2 Level Fusion: Small Kit (2.8cc)
  - o 3 Level Fusion: (4.2 cc)
  - o 4 Level Fusion: Medium Kit (5.6cc)
  - o 5 Level Fusion: (7.0 cc)

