### Rationale

Biologics are almost universally used as an adjunct in spinal fusions for osteoconductive (ability to serve as scaffold for bone growth), osteoinductive (ability to stimulate bone growing cells), and osteogenic (bone growth cells creating new bone) effects. However, the use of BMP is marginally very expensive and has well documented complications such as cancer, wound complication, and increased immediate post-operative pain. BMP is a commonly used adjunct for minimally invasive surgeries of the lumbar spine for its osteoconductive, osteinductive, and osteogenic effects without the need for autologous bone graft. Recent studies, specifically the study by [name]. using BMAC with allograft, and the study by Gan et al. using BMAC with beta-tricalcium phosphate during spinal fusion procedures have produced positive results comparable to BMP results. In addition, several recent studies using BMAC to treat bone non-unions and osteonecrosis (abnormal bone death) have been positive. Therefore, it is believed that BMAC with allograft has the same osteoconductive, osteoinductive, and osteogenic effects as BMP without including the same complications. Previous research conducted at our own institution has demonstrated clear efficacy in the usage of bone marrow aspiration and concentration for the treatment of high risk adult spinal deformity patients relative to iliac crest, in a randomized manner. This has been tremendously helpful in our attempt to reduce inefficiencies in the cost of patient. This study intends to further investigate and compare the efficacy and long term effects of anterior lumbar spinal fusions with BMAC and allograft to that of BMP in 2-4 level lumbar spine surgical cases. This study also attempts to enhance our understanding of the cellular mechanisms that correlate with outcomes, a point of deficiency in previous studies, by adding a cellular analysis component. Use of BMAC and allograft may be an alternative to BMP that will limit BMP's increased price, known increase of complications, and foreign antibodies. It is anticipated that there will be an increase in minimally invasive spine surgeries for lumbar degenerative disease which will expand the role and use of biologics due to suboptimal successful fusion rates without their usage. This increase in minimally invasive surgery has been reflected in the busy practices of the coinvestigators of this trial who wish to study the comparative efficacy of the 2 main biologics currently in use as their standard practice.

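### The BMP arm's instruction gives a flat 12 mL and then a by-level schedule of 1.4 to 7.0 cc, and the two cannot both be followed

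*Combined protocol and SAP*

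**What the plan says.** The rhBMP-2 Fusion section, under Research Design & Methods, gives the amount of BMP twice.

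- First as a single volume: "For patients selected to receive BMP, 12 mL BMP will be applied at the surgical site of the interbody fusion using a collagen sponge". The sentence ends by referring to the manufacturer's directions. It does not mention the number of levels.
- Then as a list of kit use by number of levels: "1 Level Fusion: Extra small kit (1.4 cc"), "2 Level Fusion: Small Kit (2.8cc"), 4.2 cc for three levels with no kit named, "4 Level Fusion: Medium Kit (5.6cc"), and "5 Level Fusion: (7.0 cc") with no kit named.

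Three other places bear on the point. The Rationale describes the comparison as one with "BMP in 2-4 level lumbar spine surgical cases". The Intervention section requires "INFUSE rhBMP-2 Bone Graft used according to its approved FDA labels". Research Design & Methods states: "All procedures are approved by the FDA (see appendix A for approved labeling"). None of these gives a volume, and Appendix A is not in the text available for this review. No other section states a BMP volume.

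**The concern.** A surgeon or coordinator reading this section meets two different amounts for the same product at the same site, with no sentence saying that one is a maximum, a total over several sites, or a different quantity. This is an operative instruction for one of three randomised arms.

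The product's complications are part of the reason for the trial (Rationale), and they are listed again under Adverse Events/Risks. Fusion status and complications are outcomes, and complication and pseudarthrosis rates feed the stopping criteria (Criteria for Action). Reading the BMP results requires knowing how much was meant to be implanted. Protocol compliance is to be monitored, and it cannot be checked against two incompatible amounts.

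**Working it through.** **Inputs**, all from the rhBMP-2 Fusion section: a flat volume of 12 mL, and schedule entries of 1.4, 2.8, 4.2, 5.6 and 7.0 cc for 1 to 5 levels. The target case mix of 2 to 4 levels comes from the Rationale. 1 mL = 1 cc.

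**Step 1: the form of the schedule.** 1.4/1 = 2.8/2 = 4.2/3 = 5.6/4 = 7.0/5 = 1.4. The schedule is exactly 1.4 cc × levels. That regularity makes a garbled list unlikely and suggests that the entries are patient totals.

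**Step 2: 12 mL against the entries, both as patient totals.**

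| Levels | Schedule (cc) | 12 ÷ schedule | 12 − schedule (mL) |
|---|---|---|---|
| 1 | 1.4 | 8.57 | 10.6 |
| 2 | 2.8 | 4.29 | 9.2 |
| 3 | 4.2 | 2.86 | 7.8 |
| 4 | 5.6 | 2.14 | 6.4 |
| 5 | 7.0 | 1.71 | 5.0 |

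No entry equals 12. At 1.4 cc per level, 12 mL would need 12/1.4 = 8.57 levels, and the list stops at five.

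**Step 3: 12 mL as an amount per level.** 12/1.4 = 8.57 times the schedule. Totals would be 24, 36 and 48 mL at 2, 3 and 4 levels, against 2.8, 4.2 and 5.6 cc. The sentence does not say per level, so this reading is only a possibility.

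**Step 4: schedule entries as amounts per level, multiplied by levels.** The list's heading could be read this way. Totals: 1 × 1.4 = 1.4; 2 × 2.8 = 5.6; 3 × 4.2 = 12.6; 4 × 5.6 = 22.4; 5 × 7.0 = 35.0. None is 12, though the three-level total comes close. On this reading a flat 12 mL would be 12/5.6 = 2.14 times the two-level total but only 12/22.4 = 0.54 of the four-level total, so it still fails as a general rule.

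**Step 5: combinations of the named kits.** 1.4, 2.8 and 5.6 cc are all multiples of 1.4. Eight units give 11.2 cc and nine give 12.6 cc. No combination gives 12.

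**Step 6: a lost decimal point (1.2 mL).** Per level, 1.2/1.4 = 0.857, which is 14% low. As a patient total, 1.2/2.8 = 0.43, 1.2/4.2 = 0.29 and 1.2/5.6 = 0.21. It matches no entry.

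The 12 mL figure is not reproduced under any reading tried.

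**The case against.** The strongest reply is that the label already governs the amount. The 12 mL sentence defers to the manufacturer, the Intervention section requires on-label use, and Appendix A is cited for the labelling. A specific kit list follows the general sentence at once, and the treating surgeon presumably knows the kits. This lowers the practical risk that 12 mL would be implanted, and no such event is claimed here. It does not remove the conflict: the label can show which figure is right but cannot make both right, and the written protocol would still need changing.

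A typing or extraction slip is also possible. A lost range mark (1 to 2 mL) would bracket the single-level 1.4 cc, but not the multi-level totals in the target case mix. If 12 is a slip, the ratios above do not apply, but the sentence is still wrong as printed.

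Two narrower objections stand in part. The 8.6-fold figure rests on a per-level reading that the sentence does not state, so it should carry little weight. The absence of a field for implanted volume is not established, because the case report forms appear by title only. Levels and product used may also be recoverable from chart review, planned-procedure data and intra-operative data. Explicit fields are therefore an optional improvement.

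**Conclusion.** The inconsistency holds and must be fixed. The section gives two amounts that cannot both be followed, and nothing in the available text reconciles them. If both figures are read as patient totals, 12 mL is 2.1 to 4.3 times the schedule over the 2 to 4 levels the study targets, or 6.4 to 9.2 mL more. It is 5.0 mL above the schedule's five-level maximum.

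This assumes that the entries are totals and that 12 mL measures the same thing as the kit volumes. The ratios are of volume; milligram doses cannot be derived because no BMP concentration is stated. The documents do not show which figure is intended, so no corrected value can be offered. The point does not enter any sample size, power or alpha calculation.

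**What to change.** 1. Check both figures against the approved labelling (Appendix A and the product label).
2. Keep one rule. If the labelling confirms the by-level schedule, delete or correct the 12 mL sentence. Suggested wording: *BMP will be placed at the interbody site on a collagen sponge, as the manufacturer directs, in the volume listed below for the number of levels fused.*
3. State whether the listed volumes are patient totals. If 12 mL measures something other than kit volume, say what it measures.
4. Optionally, make BMP volume implanted and number of levels explicit fields in the intra-operative data already being collected, so that fusion and complications in this arm can be tied to the amount used.

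The cost is one corrected sentence with a short clarification, and two data fields if wanted, in a single protocol amendment. No patients, visits or tests are added.

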#### **Control Fusion**

• As per standard of care, the control group will receive 15cc – 45 cc of allograft with autograft and bone marrow aspirate at each level. The iliac crest is the common donor site

PI: [name]

for autograft. Bone marrow aspirate will also be processed for data collection. Both will be harvested and combined in routine fashion to make the bone graft.

• Using the standard technique for anterior lateral fusion, the bone graft will be laid onto the desired site of fusion.

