# **Purpose of Study and Background**

# **Purpose of the Study**

The aim of this investigation is to compare the use of bone marrow aspirate concentrate (BMAC) and allograft versus recombinant human bone morphogenetic protein-2 (BMP) versus the gold standard fusion in subjects undergoing elective lumbar spinal fusion with interbody support. The safety and efficacy of the surgical interventions will be evaluated by assessing fusion status and subjects' quality of life outcomes.

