
For validity and to provide reference the 2 main biologics will be controlled with the auto graft gold standard fusion. In some applications, such as intervertebral disc fusion in the cervical and lumbar spine, allografts with internal fixation have rivaled the results of autogenous bone grafts. Studies by Bishop et al., Martin et al., and Zdeblick and Ducker have shown that using allograft bone in the anterior cervical spine during fusions is just as adequate as autograft bone. In addition, Savolainen et al. observed similar rates of fusion in autograft and allograft. Also, in the lumbar spine, anterior femoral ring allografts have been very successful when posterior instrumentation is

PI: [name]

used. Also, posterior spinal fusions for scoliosis in adolescents have similar rates of fusion when comparing allograft and autograft. Still further comparison is needed and a study comparing autograft as a control in BMAC vs. BMP will fill a gap in the literature.

The high expense and limited indication of BMP products makes it necessary to apply for prior authorization from insurance companies of these products for usage by insurance companies. For the purposes of this study, standard of care in all aspects will be followed, and pre-operative authorization for use of BMP as well as BMAC will be obtained from insurance companies prior to the day of surgery. If authorization cannot be obtained prior to the day of surgery the subject enrolled will be counted as a screen fail. While both of these products are currently approved for use by the NYU/HJD operating room product and pricing committees, through the conduction of this research we will also be working with the NYULMC supply chain management team in vetting and determining the clinical cost effectiveness of these biologics.

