# **Study Objective**

To compare the efficacy of BMAC+allograft versus BMP versus autograft (control), we plan to pursue a prospective, blinded controlled study in which: BMAC+allograft or BMP or autograft will be randomized 1:1:1 ratio, respectively to certain patients undergoing a lumbar fusion by interbody support.

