# **Study Design**

This study will be a prospective, randomized clinical study at a single-center, NYU Langone Medical Center. It is intended to compare and evaluate the efficacy of subjects who are either treated with (1) bone marrow aspirate concentrate (BMAC) and allograft or (2) recombinant human bone morphogenetic protein-2 (BMP) or (3) autograft (control) during lumbar spinal fusion with interbody support. The clinical, radiographic, and Health Related Quality of Life (HRQOL) outcomes will be assessed in operatively treated adult spinal degenerative disease patients undergoing lumbar spinal fusion.

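### The only instruction for building the control graft includes allograft, while six other sections describe the control as autograft, autograft with aspirate, or iliac crest graft

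*Combined protocol and SAP*

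**What the plan says.** Purpose of the Study sets the two biologics "versus the gold standard fusion in subjects undergoing elective lumbar spinal fusion with interbody support". Rationale identifies that standard: "the 2 main biologics will be controlled with the auto graft gold standard fusion". It also gives the reason for having the arm: "a study comparing autograft as a control in BMAC vs. BMP will fill a gap in the literature".

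Study Objective repeats the label: "BMAC+allograft or BMP or autograft will be randomized 1:1:1 ratio". Study Design lists the third arm as "3) autograft (control) during lumbar spinal fusion with interbody support". Research Design & Methods and the list of three grafts under Intervention add bone marrow aspirate to the autograft. Criteria for Action calls the control the current gold standard of iliac crest graft and ties a stopping rule to it, a 10% reduction in fusion rate relative to control.

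Control Fusion is the only section that tells the surgeon what to implant. It cites standard of care and says "the control group will receive 15cc – 45 cc of allograft with autograft and bone marrow aspirate at each level". It names the iliac crest as the common donor site for autograft, notes that aspirate is also processed for data collection, and ends the step with "Both will be harvested and combined in routine fashion to make the bone graft". It gives no separate autograft volume or share.

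**The concern.** An operative treatment instruction disagrees with the stated comparator. The investigational arm is itself allograft-based (BMAC + allograft), so whether the control contains allograft decides what the trial compares. If it does not, BMAC + allograft is set against the patient's own bone with aspirate. If it does, two of the three arms contain allograft and differ in what is added to it.

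The study hypothesis is that BMAC + allograft will be similar to the BMP and control groups, and the primary outcome is 1-year fusion on CT. Similarity to a control that contains allograft is a different conclusion from similarity to autograft. The second is the gap that Rationale says the trial will fill.

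**Working it through.** The plan gives no figure to reproduce here, and the point depends on no sample size, power or alpha. The check sets the descriptions side by side.

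| Section | Control described as | Allograft named in control? |
|---|---|---|
| Rationale | autograft, as gold standard | no |
| Study Objective | autograft | no |
| Study Design | autograft | no |
| Research Design & Methods | autograft plus aspirate | no |
| Intervention (list of grafts) | autograft plus aspirate | no |
| Criteria for Action | iliac crest graft, as gold standard | no |
| Control Fusion | allograft with autograft and aspirate, 15–45 cc, per level | yes |

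1. **What conflicts.** Aspirate is not the problem, because two of the six labels already include it. Only the allograft is new in Control Fusion.

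2. **Does Control Fusion agree with itself?** The sentence "Both will be harvested and combined in routine fashion to make the bone graft" refers to two harvested materials. The two sentences before it concern autograft from the iliac crest and bone marrow aspirate, and both come from the patient. Allograft does not: the BMAC procedure under Intervention says it comes from the bone bank. Read alone, the mixing sentence describes autograft plus aspirate, which matches Research Design & Methods and Intervention. The sentence giving the volume does not.

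3. **What the volume refers to.** The 15–45 cc may be allograft with autograft added, or the whole mixture. It may also be a figure meant for another material, if allograft is a slip. The amount of autograft is unstated in every case.

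4. **Consequence of each reading.**
   - Allograft intended, on either reading of the volume: the control shares allograft with the BMAC + allograft arm, and the six descriptions are incomplete.
   - Allograft a slip: the six descriptions stand, and the operative instruction is the text in error.

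5. **What would be recorded.** The intra-operative measures under Intervention are blood loss, length of stay, bone marrow quality and complications; the later outcome list repeats these without marrow quality. Neither lists graft source or graft volumes.

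**The case against.** The strongest reply is that this is a one-word erratum. The Intervention list, Research Design & Methods and the mixing sentence all point to autograft plus aspirate. This stands in part: the slip is a serious possibility and perhaps the likelier one. It does not remove the point, because the sentence that may be wrong is the one the surgeon follows.

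A second reply is that Control Fusion appeals to standard of care, and Adverse Events/Risks calls allograft as a graft extender acceptable practice. That remark is general, is followed by a comparison of allograft with BMP, and is not tied to the control arm. No section describes the control as extended autograft. If that is the intention, the labels need to say so.

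A reader might also draw four stronger conclusions that the documents do not support:

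- *The gold-standard label is false.* It holds if allograft is a slip. If allograft is intended, the graft still contains autograft, with the iliac crest as the common donor site, so the label is incomplete and reporting could state the actual composition.
- *The planned data could not show what was implanted.* The lists under Intervention are measures, not every data field. Data Storage and Confidentiality plans hospital chart review, Data Monitoring assigns intra-operative data collection, and the contents of the case report forms are not shown. Only the absence of graft volumes from the listed measures is established.
- *Allograft in the control biases the fusion comparison.* Adverse Events/Risks says allograft is incorporated more slowly and less completely. Rationale reports, for example, that "posterior spinal fusions for scoliosis in adolescents have similar rates of fusion when comparing allograft and autograft". Nothing gives the effect of adding allograft to autograft.
- *The 10% stopping rule cannot be applied.* It uses the concurrent control arm and can still be computed; only its description of that arm is in doubt.

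**Conclusion.** The point holds as an inconsistency between the operative instruction and six other descriptions of the control. The mismatch is plain in the current text. Which side is wrong cannot be determined from the documents.

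The consequence is conditional. If Control Fusion is followed literally, the control arm (20 of 60 planned patients) shares allograft with the BMAC + allograft arm. The two of three pairwise comparisons that involve the control should then not be labelled comparisons with autograft or iliac crest graft alone. The randomised comparison between the arms as treated remains valid. No numerical effect is attached: with no autograft amount stated, any estimate of the allograft share would rest on invented inputs.

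**What to change.** Decide what the control graft is and say the same thing everywhere.

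- **If allograft is a slip:** delete it from Control Fusion. Do not carry the 15–45 cc over as a required iliac crest harvest, since Adverse Events/Risks lists donor-site pain, bleeding and infection.
- **If allograft is intended:** name the arm *autograft extended with allograft, plus bone marrow aspirate* in Rationale, Study Objective, Study Design, Research Design & Methods, Intervention and Criteria for Action. Remove the iliac crest gold-standard label from Criteria for Action.
- **In either case:** add the autograft source, and the autograft and allograft cc per level, to the intra-operative measures under Intervention.

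A minimum autograft volume or a cap on extender is not recommended. The documents give no figure for either, and imposing one could change surgery and increase donor-site harm.

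The cost is a wording amendment plus one source entry and two volumes per level on the intra-operative record. Visits and sample size do not change. If allograft stays, the trial gives up the claim to a pure autograft gold-standard comparison.
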